11.2 Adverse Events

The Investigator is responsible for monitoring the safety of patients who have enrolled in the study and for accurately documenting and reporting information as described in this section. Patients will be instructed to report to the Investigator any AE that they experience. Investigators will ask about the occurrence of AEs at each visit. Investigators are required to document all AEs occurring during the clinical study, commencing with the first dose of IMG-7289 through to the End of Study Visit (scheduled at 28 days post last IMG-7289 dose). Adverse event recording will continue for patients

who discontinue study treatment early but remain in follow-up, until their End of Treatment, Pre-End of Study and End of Study Visits have been completed.

Note: Any medical event which occurs from the time of Informed Consent but prior to dosing with IMG-7289 must still be documented in the patient's medical notes and will be recorded on the appropriate medical history CRF pages.

Adverse events will be recorded on designated CRF pages. Each AE is to be characterised (i.e., verbatim term) and information provided regarding its seriousness, start and stop dates, intensity, outcome, and causal relationship with the study drug.

An AE is any undesirable physical, psychological or behavioral effect experienced by a patient during participation in an investigational study, in conjunction with the use of the drug or biologic, whether or not product-related. This includes any untoward signs or symptoms experienced by the patient from the time of first dose with IMG-7289 until completion of the study.

Adverse events may include, but are not limited to:

- Subjective or objective symptoms spontaneously offered by the patient and/or observed by the Investigator or medical staff
- Findings at physical examinations
- Laboratory abnormalities of clinical significance

Progression of underlying malignancy is not reported as an AE if it is consistent with the suspected progression of the underlying cancer. Clinical symptoms of progression may be reported as AEs if the symptom cannot be determined as exclusively due to the progression of the underlying malignancy or does not fit the expected pattern of progression for the disease under study. If there is any uncertainty about an AE being due to only the disease under study, it should be reported as an AE.

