11.2.3 Serious Adverse Events

Serious adverse events will be reportable from the time the time of first dose through the End of Study Visit (scheduled for approximately 28 days post last IMG-7289 dose) **or** until the Investigator and Imago BioSciences determine that follow-up is no longer necessary. Serious adverse events that are suspected to be drug related will be reported even if they occur when the patient is no longer on the study.

An SAE is any AE that results in any of the following outcomes:

- Death[‡]
- Life-threatening experience
- Required or prolonged inpatient hospitalisation[‡]
- Persistent or significant disability/incapacity
- Congenital anomaly
- Important medical events that, based upon appropriate medical judgment, may jeopardise the patient and may require medical or surgical intervention to prevent one of the outcomes listed above.

Life-threatening experience. Any adverse event that places the patient, in the view of the reporter, at immediate risk of death from the adverse event as it occurred, i.e., does not include an adverse event that had it occurred in a more severe form, might have caused death.

Required or prolonged inpatient hospitalisation. The adverse event resulted in an initial inpatient hospitalisation or prolonged an existing hospitalisation of the patient. If a patient is hospitalised as part of the clinical use of the product, a period of normal hospitalisation will be outlined in the protocol or by the judgment of the Investigator. Hospitalisations longer than this period will be prolonged hospitalisations.

Persistent or significant disability/incapacity. An adverse event that resulted in a substantial disruption of a person’s ability to conduct normal life functions.

Congenital Anomaly. The exposure of the patient to the drug or biologic during pregnancy that is

judged to have resulted in the congenital anomaly/birth defect.

Important medical events. Adverse events that may not result in death, be life-threatening, or require hospitalisation may be considered a serious adverse event when, based upon appropriate medical judgment, may jeopardise the patient or subject and may require medical or surgical intervention to prevent one of the outcomes listed above. Important medical events or interventions may be considered an SAE based upon medical judgment of the Investigator.

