The statistical analyses will be reported using summary tables, figures, and data listings. Unless otherwise noted, all statistical testing will be two-sided with significance being $p < 0.05$. Continuous variables will be summarized with means, standard deviations, medians, minimums, and maximums. Categorical variables will be summarized by counts and by percentage of patients in corresponding categories. As appropriate and where specified, continuous and categorical variables will be evaluated using the Student t-test, ANOVA, Wilcoxon rank sum, Fisher's exact, or χ^2 tests. As appropriate and where specified, summary tables will be presented by cohort, and may also include a "Total" or "All Patients" summary.

The analyses described in this plan are considered *a priori*, in that they have been defined prior to database lock. If any post-hoc analyses are performed they will be defined and reported in the CSR.

All analyses will be performed using SAS statistical analysis software (SAS, SAS/GRAPH and SAS/STAT; version 9.3 or higher of SAS for Windows [SAS Institute Inc; Cary, NC, USA]).

A. Data Sources

All data are collected *via* electronic case report forms (eCRFs) through remote data entry. Section 13.7 of the protocol describes data quality assurance.

B. Definition of Baseline

For analysis purposes, baseline is defined as the last assessment prior to the first dose of study drug. Cycle 1 Day 1 is the first day a patient receives study drug. For most measurements, baseline assessments will be taken pre-dose on Cycle 1 Day 1. If pre-dose assessments on Day 1 are not available, the most recent prior assessment closest to Day 1 may be substituted in some cases, and unless otherwise specified. For local laboratory data, baseline data will be obtained during the screening period (Days -28 to 1). All other baseline data will be collected on Days -21 to 1.

C. Missing Data

For safety and tolerability, missing data, including those not obtained because of death, will be the last value carried forward.

If CTCAE Grade is missing, the event is assumed to be 'Severe' (grade 3). If AE relatedness is missing, the event is assumed to be 'possibly' related.

Otherwise, missing data will not be replaced with imputed values. When relevant, sections below will address how missing data will be handled for the particular analyses.

D. Display and Imputation Methods for Missing Dates

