- Therapies that are not marked as ongoing, and have a stop date with a missing day and month will be assumed to occur on the *last* day of the non-missing year (i.e. December 31).

For the listings, AE, CM and PCTHX dates will be listed as collected in the eCRF. All other data will be reported as they are collected. No imputation methods will be used to replace missing data unless otherwise stated in this document.

Partial transfusion start dates are not permitted, and thus assumptions should not be needed to determine if the transfusion was prior to the first dose of IMG-7289.

E. Multiple Study Centers

There will be no adjustment for multiple study centers in the analysis.

F. Covariate Adjustment in Primary Analysis

There will be no adjustment in the analysis for covariates.

G. Sample Size Reassessment

No sample size reassessment is planned for this study.

H. Interim Analyses or Timing of Analyses

The Data Safety Monitoring Committee (DSMC) will review safety parameters, pharmacodynamic markers, and pharmacokinetic parameters to draw conclusions around the safety and pharmacodynamic effect of differing doses, treatment regimens and dosing durations. DSMC reviews are critical, as neither a new dose-finding sub-cohort, nor a duration-finding cohort may commence without DSMC review and recommendation to do so. Refer to Protocol Section 8 for details pertaining to DSMC reviews, and management of study toxicities.

I. Multiple Comparisons

No control for the effect of multiple comparisons is planned.

J. Analysis Populations

Two analysis populations will be defined for use with various analyses.

1. Safety Population

All enrolled patients who received at least one dose of IMG-7289 will be included in the Safety population.

2. Efficacy Population

All enrolled patients who received at least one dose of IMG-7289 and have disease assessment at baseline (Bone Marrow Aspirate/Biopsy and Haematology). Patients having no post-baseline response assessment will be defined as NE (Not Evaluable).

K. Data Display Characteristics

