guidelines change, or are not followed adequately, treatment-emergent events will be identified programmatically per the above definition, using imputed start date.

Severity of AEs will be reported using the NCI CTCAE grades (v4.03) where Grade 1 is Mild, Grade 2 is Moderate, Grade 3 is Severe, Grade 4 is Life-Threatening, and Grade 5 is Fatal.

CCI

CCI

B. Other Safety Parameters

Changes in vital signs, laboratory values and ECGs will also be evaluated and assessed. Information on the timing of these assessments is presented in Protocol Section 9.

The following laboratory tests will be conducted:

- Complete blood counts (CBC) and differential
- Coagulation
- Chemistry panel including LFTs (AST, ALT, INR, total bilirubin, gamma glutamyltransferase (GGT), and albumin)
- Urinalysis with microscopy
- ECGs

Laboratory values will be listed and summarized at each assessment. Numerical laboratory results will be summarized with the actual values, change from baseline (CFB), percent CFB by visit. P-value for test to assess maximum and minimum change from baseline within each cohort will be calculated using paired t-test.

Shift tables for laboratory values with respect to normal range (low, normal, high) and CTCAE toxicity grade, compared to baseline, will be summarized by visit. Overall laboratory result shift from baseline (Normal, Abnormal clinically significant (CS), and Abnormal non-clinically significant (NSC)) will be summarized.

ECG parameters and vital sign assessments will be summarized with the actual values, change from baseline, and percent change from baseline by visit. P-value for test to assess maximum and minimum change from baseline within each cohort will be calculated using paired t-test. Additionally, overall ECG result shift from baseline (Normal, Abnormal clinically significant (CS), and Abnormal non-clinically significant (NSC)) will be summarized.

Physical exam data will be listed.

X. Additional Analysis

The additional analyses outlined here will be performed using the Safety Population.

A. Pharmacodynamics

Pharmacodynamics (PD) obtained from serial blood, bone marrow, and urine sampling at specified time points will be listed and summarized.

CCI

CCI

CCI

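### As the readable text stands, the SAP sets every missing CTCAE grade to Grade 3, with no exception for an adverse event recorded as fatal or life-threatening

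*SAP*

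**What the plan says.** SAP VI.C gives two imputation rules for adverse events. For severity: "If CTCAE Grade is missing, the event is assumed to be 'Severe' (grade 3". For causality: "If AE relatedness is missing, the event is assumed to be 'possibly' related". Neither carries a condition. The section adds that later sections will deal with missing data where relevant. SAP VI.D closes off other routes: "No imputation methods will be used to replace missing data unless otherwise stated in this document".

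SAP IX.A labels the top of the severity scale: "Grade 3 is Severe, Grade 4 is Life-Threatening, and Grade 5 is Fatal". It also says that a patient with repeated occurrences of the same AE is counted once, at the highest grade. The text directly after the scale is redacted.

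Protocol 11.2 requires that each AE be characterised, with "information provided regarding its seriousness, start and stop dates, intensity, outcome, and causal relationship with the study drug". Protocol 11.2.3 introduces the serious criteria with "An SAE is any AE that results in any of the following outcomes", and the list includes death and a life-threatening experience. Under SAP III.A, deaths and SAEs are also collected on a separate form.

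**The concern.** Filling a blank with Grade 3 is cautious when the true grade is 1 or 2. It is a downgrade when the true grade is 4 or 5. For a fatal or life-threatening event the information needed to avoid the downgrade should already be in the database, because outcome and seriousness are collected as well as intensity. The rule as written does not consult them.

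The companion rule for causality shows that caution was the aim: a missing relationship becomes possible, and Protocol 11.2.2 counts possible as related. The grade rule misses that aim for the most severe events.

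At stake is the internal consistency of the safety report. Safety and tolerability is a primary objective, and severity is one of the named ways in which AEs are assessed. A severity summary that shows Grade 3 for an event listed among the deaths would have to be explained.

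**Working it through.** No figure in the documents depends on this rule, so there is nothing to reproduce. The check is a reading of the rule against the other AE fields, followed by an illustration of size.

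**Reading**

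1. Rule (SAP VI.C): grade missing → Grade 3, no condition.
2. Scale (SAP IX.A): life-threatening = 4, fatal = 5.
3. Other fields (Protocol 11.2 and 11.2.3; SAP III.A): outcome and seriousness for each AE, plus a separate form for deaths and SAEs.
4. Take an AE with a fatal outcome and a blank grade. Step 1 gives Grade 3; steps 2 and 3 point to Grade 5. The two conflict, and no readable sentence says which prevails.
5. Highest-grade rule (SAP IX.A): if the patient has another recorded Grade 4-5 occurrence in that category, it is the one tabulated and the error may not show. If not, the imputed 3 is tabulated.

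**Size of one such case**

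Inputs: minimum cohort of 3 and about 40 patients in total (SAP IV.C). Assume one patient whose only Grade 4-5 event is fatal or life-threatening and ungraded, and no other patient with a Grade 4-5 event. Incidence is x/n with an exact (Clopper-Pearson) 95% interval.

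| | Current rule | Grade taken from outcome or seriousness |
|---|---|---|
| n = 3 | 0/3 = 0% (0 to 70.8%) | 1/3 = 33.3% (0.8 to 90.6%) |
| n = 40 | 0/40 = 0% (0 to 8.8%) | 1/40 = 2.5% (0.06 to 13.2%) |

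A count of patients at Grade 3 or higher is the same under both rules.

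**How often**

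The documents give no rate for Grade 4-5 events or for missing grades, so both are assumptions. Let p be the proportion of patients with a Grade 4-5 event and m the chance that such a patient is downgraded because the grade is blank.

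- Expected number downgraded = 40 × p × m
- Chance of at least one = 1 − (1 − p × m)^40

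| p | m | Expected | Chance of at least one |
|---|---|---|---|
| 20% | 1% | 40 × 0.002 = 0.08 | 1 − 0.998^40 = 7.7% |
| 40% | 2% | 40 × 0.008 = 0.32 | 1 − 0.992^40 = 27.5% |
| 60% | 10% | 40 × 0.06 = 2.4 | 1 − 0.94^40 = 91.6% |

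These figures are best read as upper-side illustrations. They cover every Grade 4-5 event and take missingness to be the same at all severities. The point here concerns only events that another field marks as fatal or life-threatening, which are the events least likely to keep a blank grade.

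**The case against.** The strongest objection is that the absence of an exception is not fully established. SAP VI.C defers to later sections, and the relevant one, IX.A, is redacted just after the scale. That stands, and it is why the point is confined to the readable text.

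Other objections narrow it further:

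- **Controls.** Intensity is required for each AE. SAEs are reported within 24 hours, and fatal or life-threatening events prompt immediate contact with the sponsor (Protocol 11.2.4). Monitors check the forms for completeness (13.6), and the investigator signs once queries are resolved (14.4). A blank grade on such an event should be rare. The SAP's own explicit commitment to query, however, covers missing dates only (VI.D).
- **Where the field sits.** The case report form is not in the documents. The life-threatening criterion may be on the SAE form and not on the AE page, so the repair has to name both.
- **Seriousness is not grade.** Protocol 11.2.3 treats life-threatening as the reporter's view of immediate risk of death. That is close to Grade 4, but the documents never equate the two. Using it for imputation is a reasonable convention, not a certainty.
- **Direction.** The rule overstates every blank event that is truly Grade 1 or 2. It errs the other way only at Grade 4-5.

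A reader might infer more: that severe toxicity is under-reported by rule, that deaths are understated, or that dose escalation could be misled. The documents do not support this. Deaths and SAEs are captured on their own form. Data other than AE, medication and chemotherapy dates are listed as collected (SAP VI.D), so a blank grade should stay visible. DLTs rest on the investigator's assessment and DSMC review during the trial (Protocol 8.1 and 8.2.1), and nothing says that an imputed grade feeds either.

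**Conclusion.** The point holds as a small defect in a stated rule. On the readable text, a fatal or life-threatening AE with a blank grade becomes Grade 3. If the patient has no other recorded Grade 4-5 occurrence in that category, the summary by grade understates severity and conflicts with the death and SAE data.

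The effect is one patient at a time: 33.3 percentage points in a cohort of three, 2.5 points in 40, and none on a count of Grade 3 or higher. The conclusion assumes that no exception lies in the redacted part of SAP IX.A and that severity is summarised in a way that separates Grade 3 from Grades 4 and 5; no readable sentence specifies a Grade 4-5 incidence table. Frequency cannot be estimated from the documents, but the controls suggest that it is low. The change is worth making because it is cheap, not because the trial's conclusions are shown to depend on it.

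**What to change.** Replace the grade sentence in SAP VI.C with a conditional rule:

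- Query every missing CTCAE grade.
- If the grade is still missing, assign Grade 5 when the AE outcome is fatal.
- Otherwise assign Grade 4 when the AE or SAE form records the event as life-threatening.
- Otherwise assign Grade 3.
- Flag every imputed grade in the AE listings.

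If the redacted part of SAP IX.A already contains such an exception, a cross-reference from VI.C is enough. The SAP already imputes conditionally elsewhere: in VI.D, treatment-emergent status for an AE with a missing start date depends on its end date and the first-dose date.

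The cost is one SAP sentence, one programming condition, a check on which form holds the life-threatening field, and a flag variable. The SAP can be modified until database lock (I.B), and nothing in trial conduct changes.

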6.2 Patient Enrollment

A sufficient number of patients who fulfil the inclusion and exclusion criteria documented in Section 6.1 will be screened to ensure approximately 40 patients are enrolled and treated in this study. As patients are screened and become eligible for the study, they will be assigned to the currently open cohort. This process will be detailed in the Study Reference Manual (SRM).

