The patient population will consist of men and women age 18 or older who have been diagnosed with either high-risk Acute Myeloid Leukaemia or Myelodysplastic Syndrome. Eligible patients who have signed informed consent must not have had prior treatments within a specified period of time and must have meet pre-specified laboratory values for selected parameters, in addition to multiple other required eligibility criteria.

C. Sample Size Predictions

This study is designed to make an assessment of the safety, tolerability, and single-dose pharmacokinetics of the capsule formulation of IMG-7289, with and without ATRA. With the planned minimum number of patients per dose cohort/sub-cohort (N=3), the study is sufficiently powered to determine mean pharmacokinetic parameters. When feasible, more patients will be added to each cohort/sub-cohort. Approximately 40 patients with high risk AML/MDS patients will be enrolled and treated in this study.

D. Treatment Randomization

This is not a randomized study.

E. Assessment Schedule

The study assessments depend upon the cohort and the recommendations of the DSMC. Further description is available in the Protocol Sections 9 and 16.1.

V. Interventions

A. Clinical Trial Material

CCI
CCI
[REDACTED] IMG-7289 will be supplied in capsules of multiple strengths. These strengths, based on IMG-7289 free base, i.e. the active substance, may include: 5 mg, 10 mg, 25 mg, and 50 mg. Additional strengths may be added over the duration of the study.

ATRA will be supplied as oval, soft gelatin capsules; one half of each capsule is opaque orange-yellow and the other half opaque reddish brown. One capsule strength will be provided: 10 mg. In addition to ATRA, the capsule contents are beeswax-yellow, soya oil-hydrogenated and soya oil. The capsule shell contains gelatin, glycerol, Karion 83, titanium dioxide, iron oxide yellow CII77492 and iron oxide red CI77491.

The protocol provides additional product details in Protocol Section 7.

B. Study Procedures

Patients will undergo procedures described in Protocol Section 9 to assess the study drug safety, pharmacodynamics, and pharmacokinetics in order to achieve the study objectives.

VI. General Analytical Considerations

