The assessment value, change from baseline and percentage change from baseline of these parameters will be summarized by each treatment cohort and visit. P-value for test to assess maximum and minimum change from baseline within each cohort will be calculated using paired t-test.

Additionally, maximum change from baseline, maximum percentage change from baseline, minimum change from baseline, and minimum percentage change from baseline for these parameters will be analyzed in the dose-finding cohorts separately. The treatment effect among different cohorts will be analyzed with Kruskal-Wallis tests.

B. Exposure

Exposure to IMG-7289 and ATRA will be summarized separately (i.e., by drug). Exposure will be summarized as the number of doses each patient received, as well as number of missed doses, along with the reasons for the missed doses (if feasible). Average number of cycles and total amount of time on study drug (duration of dosing in weeks) will also be summarized. Total cumulative dose, dose intensity (mg/-week, calculated as [total cumulative dose (mg-) / duration of dosing (weeks)]), and relative dose intensity (% of planned, calculated as [total cumulative dose / total planned dose] *100) will also be derived and summarized with descriptive statistics for IMG-7289 and ATRA separately.

Dose adjustments (increases and decreases), interruptions, and permanent drug withdrawals, along with corresponding reasons for each, will be summarized by study drug (IMG-7289 and ATRA).

Study drug accountability by dosage strength will be summarized based on the number of capsules of study drug (IMG-7289 or ATRA) dispensed and the number of capsules returned.

All exposure data will also be listed by cohort and patient.

C. Prior and Concomitant Medications

Prior medication is defined as any medication with a stop date prior to the date of first dose of IMG-7289. Concomitant medications are defined as medications or therapies with a start date on or after the first dose of IMG-7289. Medications may be flagged as both prior and concomitant if the start date is prior to the date of the first dose of IMG-7289 and the medication continued after the first dose of IMG-7289. The medications will be coded using the most updated version of WHO Drug at the time of study initiation (up-versioning will not occur) and will be listed by cohort and by patient. The number (%) of patients using prior, prior and concomitant, and concomitant medications will be summarized.

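### The between-cohort test of pharmacodynamic change ignores baseline in sequential, non-randomised cohorts; a baseline-adjusted analysis should be pre-specified beside it, not in its place

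*SAP*

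**What the plan says.** **The test.** For the dose-finding cohorts, SAP X.A (Pharmacodynamics) takes each marker's "maximum change from baseline, maximum percentage change from baseline, minimum change from baseline, and minimum percentage change from baseline" and continues: "The treatment effect among different cohorts will be analyzed with Kruskal-Wallis tests". SAP VI sets the threshold: "all statistical testing will be two-sided with significance being" p < 0.05. SAP VI.I plans no multiplicity control.

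**Covariates.** SAP VI.F: "There will be no adjustment in the analysis for covariates". Its heading mentions the primary analysis, but the sentence is general and X.A names no covariate. On either reading the cohort comparison is unadjusted.

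**How cohorts form.** SAP IV.D: "This is not a randomized study". Under Protocol 6.2, once patients are eligible, "they will be assigned to the currently open cohort". Protocol 6.1.1 admits both high-risk AML and high-risk MDS.

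**Baseline.** SAP VI.B: "For analysis purposes, baseline is defined as the last assessment prior to the first dose of study drug".

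**Standing of the test.** SAP II.B makes adequacy of the pharmacodynamic effect a primary objective, and III.A lists pharmacodynamic measurements among the primary endpoints. SAP VIII.A, however, analyses that objective by International Working Group response. The Kruskal-Wallis test belongs to SAP X, Additional Analysis.

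**Size.** The only statement on power is "With the planned minimum number of patients per dose cohort/sub-cohort (N=3), the study is sufficiently powered to determine mean pharmacokinetic parameters". It does not cover this comparison.

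**The concern.** Subtracting baseline removes its influence only if change is unrelated to the starting value. The documents give three reasons to expect a relation.

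- **Regression to the mean.** Protocol 6.1.1 requires platelets of at least 30 × 10⁹/L, which transfusion may achieve, and white cells of at most 30 × 10⁹/L, which hydroxyurea may achieve. Values selected at a limit, or pushed temporarily past it, tend to drift back.
- **Floor limits.** Protocol Table 11 puts marrow blasts at 5-19% in MDS with excess blasts; the note to Table 9 generally requires at least 20% for AML. A patient at 10% cannot fall by 30 points; one at 60% can.
- **Scale.** If the drug acts proportionally, absolute change depends on baseline; if additively, percentage change does. X.A tests both and does not say which governs.

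With cohorts of 3 to 5 filled in calendar order, a cohort with high starting values could show a larger fall with no drug difference, and an active cohort with low starting values could be hidden. X.A would call the first a treatment effect.

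**Working it through.** **Inputs from the documents.** Two-sided 0.05; minimum 3 per cohort; about 40 patients; up to seven dose-finding cohorts (1a to 1e in Protocol Table 1, 1χ and 1w in Table 2). Five per cohort would be 7 × 5 = 35 patients.

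**Inputs assumed.** The plan states no effect size, SD or baseline-to-follow-up correlation (ρ) for these markers, and no power figure to reproduce. I take ρ from 0.3 to 0.9, unit variance at both times, and one follow-up value per patient in place of the maximum or minimum over visits.

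**1. Precision.** Variance of change is 2(1−ρ). Residual variance after adjustment is 1−ρ². The ratio is (1−ρ²)/[2(1−ρ)] = (1+ρ)/2:

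- ρ = 0.3: 0.91/1.40 = 0.65
- ρ = 0.5: 0.75/1.00 = 0.75
- ρ = 0.7: 0.51/0.60 = 0.85
- ρ = 0.9: 0.19/0.20 = 0.95

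**2. Power.** Simulated, 4,000 runs, true cohort means spread over 2 SD:

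| Cohorts × n | ρ | Kruskal-Wallis, change | ANOVA, change | ANCOVA |
|---|---|---|---|---|
| 5 × 3 | 0.3 | 14% | 28% | 38% |
| 5 × 3 | 0.5 | 19% | 38% | 45% |
| 5 × 3 | 0.7 | 37% | 60% | 61% |
| 5 × 6 | 0.3 | 59% | 66% | 83% |
| 5 × 6 | 0.5 | 76% | 81% | 91% |
| 5 × 6 | 0.7 | 95% | 97% | 98% |

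The like-for-like comparison is ANOVA on change against ANCOVA. It gains 7 to 17 points here at ρ of 0.3 to 0.5, and 1 point at 0.7. Seven cohorts of 3 (2.5 SD effect) or 5 (2 SD effect) gave 16-19 points at ρ = 0.3, 11-12 at 0.5 and 2-3 at 0.7. At ρ = 0.9 and n = 3 the gain is nil or slightly negative. Much of the Kruskal-Wallis deficit at n = 3 is its own conservatism: its true size there is about 2%.

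**3. Direction of bias.** Let one cohort start d SD higher, with no drug effect.

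- If the difference regresses fully, expected follow-up is ρd higher. Change is biased by ρd − d = −(1−ρ)d, which is −0.5 SD for d = 1 and ρ = 0.5. The adjusted contrast is unbiased.
- If the difference persists unchanged, change is unbiased. The adjusted contrast is biased by d − ρd = +(1−ρ)d, which is +0.5 SD.

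**4. False rejection.** Seven cohorts, between-cohort baseline SD of 1 patient SD, ρ = 0.5, no drug effect. Ranges cover repeated runs.

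| Cohort difference | Test | n = 3 | n = 5 |
|---|---|---|---|
| Regresses fully | Kruskal-Wallis, change | 10% | 31-33% |
| Regresses fully | Rank ANCOVA | about 4% | about 4% |
| Persists | Kruskal-Wallis, change | about 2% | 3-4% |
| Persists | Rank ANCOVA | 8% | 12-13% |
| Persists | ANCOVA | 13-14% | 27-28% |

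With milder imbalance (five cohorts of 3, baseline means spread over 2 SD, full regression), Kruskal-Wallis rejects in only 3-6% at ρ of 0.3 to 0.7.

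**5. Proportional effects.** Seven cohorts, the same proportional effect in each, n = 3 / n = 5. For a lognormal marker with the imbalance of step 4, Kruskal-Wallis on absolute change rejects in 16% / 44%; rank ANCOVA in 4.5% / 5%; log-scale ANCOVA in 5% / 5%. For blasts, with cohorts differing only in AML/MDS mix, absolute change rejects in 10% / 25%; rank ANCOVA in 4% / 5%. Percentage change stays at 1.5-4%.

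**The case against.** A reader might infer that adjusting for baseline removes the bias and should replace the planned test. That does not follow. Without randomisation each analysis depends on how cohort differences behave over time, which the data cannot settle, and steps 3 and 4 show the result reversing when those differences persist. The AML/MDS mix is a stable patient characteristic that could well persist. Differences in prior therapy and calendar time remain under either method. This part of the objection stands in full.

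Three further points stand in part.

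- Percentage change is already planned and answers the proportional case. It does not answer regression to the mean, and nothing in X.A decides between the two scales when they conflict.
- Cohort progression rests on the Data Safety Monitoring Committee's review (Protocol 8.1), not on this p-value, so the consequence is limited to interpretation. X.A nonetheless prescribes a test at 0.05 and names its result a treatment effect.
- Baseline is scheduled for all patients, but the Safety Population used in SAP X does not require it. A change score does, however, so adjustment loses no patient who is in the planned test.

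**Conclusion.** The point holds in a limited form. The planned comparison has no protection against baseline differences between sequential cohorts where change depends on baseline. Under the assumptions shown, that can raise false rejection from a nominal 5% to about 10% with 3 per cohort and about 30% with 5. With milder imbalance and 3 per cohort there is little or no inflation.

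Two stronger inferences are not supported. One is that the primary analysis of pharmacodynamic adequacy is compromised: that objective is analysed by response under SAP VIII.A. The other is that adjustment would transform power. The wide gap between Kruskal-Wallis and ANCOVA at n = 3 mixes the baseline gain with test conservatism, and the gain depends on a correlation the documents do not give.

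The sizes also rest on a single follow-up value standing in for the maximum or minimum. The marker list in X.A is redacted, so suitability marker by marker cannot be checked. Platelets, white cells and marrow blasts are named as indicators in Protocol 8.1.

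**What to change.** - **SAP VI.F:** permit adjustment for the marker's own baseline in the pharmacodynamic comparison.
- **SAP X.A:** keep Kruskal-Wallis and add a pre-specified adjusted analysis of the post-baseline maximum or minimum value: rank ANCOVA (Quade), or log-scale ANCOVA for counts. State the scale for each marker.
- **Reporting:** show baseline values by cohort beside the results, state that neither analysis replaces randomisation, and label the p-values descriptive.
- **Interpretation:** call a cohort difference a treatment effect only if both analyses agree, including on which cohorts differ. The biases in step 3 have opposite signs, so agreement is informative. The chance that both reject cannot exceed the smaller of the two rates: about 4% when differences regress fully and 3-4% when they persist, in the step 4 settings.

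**Cost.** One degree of freedom, a little more programming, and two results per marker that may disagree. Requiring agreement also means the joint claim has no more power than the weaker test, so the gain is mainly protection against a false claim. No new data are needed, and SAP I.B allows changes until database lock.
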